**Table 2 - Data Documentation Schedule**

Assessment/ Procedure (only available data to be collected; no diagnostic or monitoring procedures to be applied to the patients apart from those of routine clinical practice)	Baseline	Treatment Period			Post-treatment (PT) Period		
		On-treatment visits	Mid treatment visit for pts receiving 24 weeks of therapy	EoT b	Early PT visit	SVR 12 visit	SVR 24 visit
Informed Consent	X a						
Demographic information	X						
Relevant CHC disease characteristics	X						
Liver fibrosis stage	X						
CHC treatment history	X						
HCV genotype and subtype	X						
HCV RNA samples	X	X	X	X	X	X	X
Clinical chemistry and hematology	X	X	X	X	X	X	X
ABBVIE REGIMEN initiation documentation c	X						
ABBVIE REGIMEN adherence		X	X	X			
Concomitant medication	X	X	X	X			
Relevant medical history, co-morbidities	X						
SAE, AE and pregnancy reporting	X	X	X	X	X d	X e	X e
For patients receiving RBV: Evidence, in accordance with local label, that female patient or female partner of male patient is not pregnant	X						
Health care resource utilization	X	X	X	X			
Patient questionnaires – WPAI, EQ5D-5L	X			X		X	X

Abbreviations: EoT = End of Treatment (at Week 12 or 24 or at premature discontinuation),

PT = Post-Treatment

- a Written informed consent must be obtained before any data documentation in the eCRF
- b Patients who prematurely discontinue should return to the site to document EoT data
- c Healthcare professional documents the type of therapy that will be initiated (12 vs 24 wks, Paritaprevir/r – ombitasvir alone vs Paritaprevir/r – ombitasvir + dasabuvir, with or without Ribavirine depending on the genotype of the virus and disease status of the patient)
- d Tolerability documentation until PT week 4
- e Pregnancy reporting for patients treated with DAA +/- RBV (see 11.1.6)

Confidential Information

No use or disclose outside AbbVie is permitted without prior written authorization from AbbVie  
 The Netherlands v 1.4 (26 March 2018). Protocol based on AbbVie shell protocol version 3.0 (22 April 2015) Page 30 of 65

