#### **9.7.3.3 Statistical Methods for Analysis of Effectiveness Variables**

The simple percentage of patients achieving SVR12 will be calculated and an exact two-sided 95% confidence interval (CI) of the percentage will be computed based on the Wilson's Score method.

Corresponding methods will be used for other response rates (EoT response rate, relapse rate, viral breakthrough). The relapse rates will be estimated in patients of the CP analysis groups with EoT response and sufficient HCV RNA measurements post-treatment. Viral breakthrough rates will be estimated in all patients of the CP analysis groups, who have at least one undetectable HCV RNA measurement on-treatment and at least one on-treatment or EoT measurement thereafter.

Univariate logistic regression methods will be used to investigate the impact of the following explanatory covariates on SVR12:

- Key demographic information
- Mode of CHC infection
- HCV RNA level at baseline
- Most recent stage of liver fibrosis
- HCV genotype and subtype (if available)
- Type of treating institute
- Liver and/or CHC related co-morbidities
- Key clinical chemistry and hematology laboratory variables at baseline

Confidential Information

No use or disclose outside AbbVie is permitted without prior written authorization from AbbVie  
The Netherlands v 1.4 (26 March 2018). Protocol based on AbbVie shell protocol version 3.0 (22 April 2015) Page 37 of 65

- In treatment experienced patients only:
  - Most recent prior treatment for CHC
  - Outcome of most recent prior CHC treatment

Further details and additional covariates will be specified in the SAP.

These analyses will be of exploratory nature, data driven, and will be repeatedly performed for various CP Analysis Groups, since not each covariate might be predictive in each patient group. Logistic regression methods will also be used to investigate the impact of treatment adherence on SVR12.

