4.2 Statistical and Analytical Methods

4.2.1 Analysis Populations and Analysis Groups

Population of Patients Enrolled [EP]

The population of patients enrolled comprises all patients who voluntarily sign and date an informed consent prior to inclusion into the study and data were captured in the eCRF.

Target Population [TP]

Patients will be included if the following applies:

- Age at least 18 years
- Confirmed CHC with genotype 1 and/or 4 only, receiving combination therapy with the interferon-free ABBVIE REGIMEN \pm RBV. The prescribed ABBVIE REGIMEN needs to be known.
- Have voluntarily signed and dated an informed consent prior to inclusion into the study
- Must not be participating or intending to participate in a concurrent interventional therapeutic trial

Core Population [CP]

The core population is defined as all patients of the target population (TP) (definition see above), who are adequately treated according to the standard of care and within local label recommendations for their specific disease characteristics (cirrhotic status, genotype). The following patients will be excluded from the CP:

- Patients with unknown fibrosis status
- Cirrhotic patients with genotype 1a not receiving ribavirin
- Patients with genotype 1 for whom 2DAA instead of 3DAA is prescribed
- Patients with genotype 4 not receiving RBV

Non-Core Population [NCP]

Patients in the TP who are not in the CP.

Core Population with Sufficient Follow-up [CPSFU {12, 24}]

In addition, the core population with sufficient follow-up data regarding SVR12 or SVR24, respectively, is defined as all CP patients,

- who have evaluable HCV RNA data ≥ 70 days or >126 days, respectively, after the last actual dose of the ABBVIE REGIMEN
- or a HCV RNA value ≥ 50 IU/mL at the last measurement post-baseline
- or had HCV RNA <50 IU/mL at the last measurement post-baseline, but no HCV RNA measurement ≥ 70 days or >126 days, respectively, after the last actual dose of the ABBVIE REGIMEN due to reasons related to safety (e.g. dropped out due to adverse event) or virologic failure (e.g. virologic failure such as relapse is reported in the electronic case report form (eCRF) but date and value of the corresponding HCV RNA test is missing).

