Virological response rates and non-response categories will be displayed for patients who completed treatment with ABBVIE regimen, as well.

SVR12 (Exploratory Analyses)

Univariate logistic regression methods will be used to investigate the impact of various explanatory covariates (patient and disease characteristics) at baseline on SVR12.

These analyses will be of exploratory nature, data driven, and will be performed for CP population.

The variables to be considered are as follows:

- Key demographic information
 - Age (continuous)

- Gender (Female [reference], Male)
 - Race/ethnic origin (White/Caucasian [reference], Black, Asian/Oriental, Other [all other races]); at least two categories with at least 10% of the patients each have to exists, so that this variable will be considered
 - Weight (continuous)
 - BMI (continuous)
 - IL28B, rs12979860 (CC [reference], CT or TT); patients with unknown genotype are excluded from the respective analyses.
- CHC disease characteristics
 - Years since diagnosis (continuous)
 - Mode of CHC infection (Drug use [reference], Other [all other answers excluding unknown], unknown);
 - Most recent stage of liver fibrosis (No cirrhosis/Transition to cirrhosis [reference], Cirrhosis; for definition see 4.2.6.2);
- HCV RNA level at baseline (\log_{10} IU/mL)
- HCV genotype(G1a*, G1b, G4; for definition see section 4.2.6.2)
- Type of treating institute (Private Practice / Private Hospital, Academic / University Hospital, General Hospital, Other)
- Co-infections (every patient not reporting the respective co-infection is considered as not having the respective co-infection)
 - HIV(No [reference], Yes)
 - HBV(No [reference], Yes)
- Liver and/or CHC related co-morbidities (every patient not reporting the respective co-morbidity is considered as not having the respective co-morbidity)
 - Liver transplantation (No [reference], Yes)
 - Steatosis (non-alcoholic) (No [reference], Yes)
 - Decompensated liver disease (No [reference], Yes)
- Other co-morbidities (every patient not reporting the respective co-morbidity is considered as not having the respective co-morbidity)
 - Depression (No [reference], Yes)
 - Diabetes mellitus (No [reference], Type 1/Type 2)
 - Hypertension (No [reference], Yes)
 - Immunologically mediated disease (No [reference], Yes)

- Hypothyroidism (No [reference], Yes)
- Alcohol use (None [reference], Yes –occasional, Yes –regular, Exdrinker)

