- Key clinical chemistry and hematology laboratory variables at baseline
 - ALT ratio (continuous, see 4.2.6.5)
 - AST ratio (continuous, see 4.2.6.5)
 - Platelets [$10^9/L$] (continuous)
- Prior treatment status (HCV treatment naïve [reference], HCV treatment experienced)
- RBV vs no RBV
- Planned treatment duration 12 wks vs 24 weeks

The categories pre-specified above could be modified in the analyses if this is supported by the data (e.g. categories could be combined, if their impact on SVR12 is similar). Furthermore, continuous variables can be replaced by categorical variables.

Adherence

Adherence will be displayed for the CP by genotype and cirrhosis status and for the SP by treatment regimen and cirrhosis status. Summary statistics (n, mean, median, standard deviation [SD], and range) will be generated for continuous variable. Numbers and percentages of patients will be presented for categorical variables.

- Adherence to ABBVIE regimen (% of target dose [adherence=cumulated number of pills taken /(initial prescribed number of pills x planned duration)])
 - >105%
 - >95%-<=105%
 - >80%-<=95%
 - >50%-<=80%
 - <=50%
- Adherence to ribavirin (% of target dose [adherence=cumulated dose taken /(initial prescribed dose x planned duration)])
 - >105%
 - >95%-<=105%
 - >80%-<=95%
 - >50%-<=80%
 - <=50%

- Percentage of actual treatment duration in relation to the target duration of ABBVIE regimen taken
- Deviating duration of ABBVIE regimen
 - Early discontinuation (actual duration is shortened for more than 7 days)
 - Not deviated
 - Exceedance (actual duration is prolonged for more than 7 days)
- Method used to document adherence (Interview, Diary)
- Percentage of actual days with treatment with RBV in relation to the planned duration
- Ribavirin earlier discontinued than ABBVIE regimen
- Initial dose of Ribavirin
 - 1000 mg/day
 - 1200 mg/day
 - XXX
- Cumulative dose of Ribavirin (g)
- Dose modifications/termination of RBV [in patients taking RBV, for a patient more than one dose modification and its main reason could be reported, but for each single reason the patient is counted only once] (Total number of patients with lower dose than highest previous dose [including patients who stopped the treatment earlier], Anemia, Nausea/Vomiting, Rash, Other [including patients who discontinued ABBVIE regimen earlier, but did not stop the RBV treatment before the ABBVIE regimen])

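### The pooled univariate odds ratios for ribavirin and planned duration on SVR12 will largely reflect patient mix and may point in a misleading direction

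*SAP*

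**What the plan says.** SAP 4.2.7.2.1, under the exploratory SVR12 analyses, states: "Univariate logistic regression methods will be used to investigate the impact of various explanatory covariates (patient and disease characteristics) at baseline on SVR12". It continues: "These analyses will be of exploratory nature, data driven, and will be performed for CP population". The covariate list that follows is mostly demographic and clinical, but ends with two treatment variables: RBV yes or no, and "Planned treatment duration 12 wks vs 24 weeks". The results go to output tis in SAP Table 7, whose title presents them as the impact of patient and disease characteristics.

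On how treatment is chosen, footnote c of Protocol Table 2 covers 12 or 24 weeks, dasabuvir or not, and therapy "with or without Ribavirine depending on the genotype of the virus and disease status of the patient". The Data Analysis part of the Protocol abstract and Protocol 9.7.2 build the CP groups on genotype 1 subtype, fibrosis status and prior treatment, because these bear on the scheduled combination and duration.

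SAP 4.2.1 excludes from the CP "Cirrhotic patients with genotype 1a not receiving ribavirin" and "Patients with genotype 4 not receiving RBV". It sets no such RBV rule for non-cirrhotic genotype 1a (G1a) or for genotype 1b (G1b), and no rule on duration.

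Protocol 9.7.3.3 lists neither treatment variable, though it allows the SAP to add covariates. It says the regressions "will be repeatedly performed for various CP Analysis Groups, since not each covariate might be predictive in each patient group". The SAP does not carry this repetition over and does not declare the change, although it declares others, such as the SVR12 upper window limit (4.1.1) and the replacement of shift tables (4.2.8.4).

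**The concern.** A univariate model for RBV compares the raw SVR12 rate of patients given RBV with that of everyone else in the CP. It describes the impact of RBV only if the two sets of patients would otherwise respond alike. By the documents' own account they would not: RBV and the longer course go preferentially to groups whose cited response rates differ from those of the remaining patients. In genotype 4 and cirrhotic G1a the CP contains no patients without RBV, so those groups enter one side of the comparison and carry no information on RBV.

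This confounding is measured and avoidable. Protocol 7.2 and SAP 1 offer the predictor analysis as a way to optimise the regimen, so an entry that makes RBV or 24 weeks look like a predictor of failure could be read as a treatment signal when it mainly describes who received what.

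**Working it through.** The plan states no odds ratio, alpha or power for these models, so there is no figure to reproduce.

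**Inputs from the documents.** SVR12 rates come from Protocol 7.1 and its Table 1.
- Non-cirrhotic treatment-naive G1a: 95-97% with RBV, 90% without.
- Non-cirrhotic treatment-naive G1b without RBV: 99%.
- Cirrhotic genotype 1, all with RBV: 92% at 12 weeks, 96% at 24 weeks.
- Genotype 4 with RBV: 100%.
- Study size: 50-55.

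**Assumptions.** The documents do not give the patient mix by genotype and cirrhosis, so it is varied. A pooled rate of 98% is assumed for non-cirrhotic patients in the duration example.

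**Within-group OR** = [p1/(1-p1)] / [p0/(1-p0)].
- RBV in non-cirrhotic G1a: (0.95/0.05)/(0.90/0.10) = 2.11, up to (0.97/0.03)/(0.90/0.10) = 3.59.
- 24 versus 12 weeks in cirrhosis: (0.96/0.04)/(0.92/0.08) = 2.09.

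**Crude RBV OR** uses the same formula on mix-weighted rates.
- *RBV has no effect.* Take 53 patients: 30 with RBV (12 non-cirrhotic G1a at 96%, 10 cirrhotic G1a at 92%, 8 genotype 4 at 100%) and 23 G1b without RBV at 99%. The RBV rate is (12×0.96 + 10×0.92 + 8×1.00)/30 = 95.7%. The OR is (0.957/0.043)/(0.99/0.01) = 0.23.
- *RBV helps G1a (90% to 97%).* Same mix: (12×0.97 + 10×0.92 + 8×1.00)/30 = 96.1%, OR 0.25. Moving 3, 6 or 9 of the 12 non-cirrhotic G1a patients to no RBV, at 90%, gives 0.50, 0.69 and 0.83.
- *Five other mixes of 52* (G1b 12-30, non-cirrhotic G1a 10-26, cirrhotic 3-20, genotype 4 4-7; RBV for all but G1b): 0.17 to 0.28. In the mix of 20 G1b, 16 non-cirrhotic G1a, 10 cirrhotic and 6 genotype 4, leaving 10% to 75% of the non-cirrhotic G1a patients without RBV gives 0.36 to 0.91.

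**Crude duration OR, 24 versus 12 weeks** (52 patients; non-cirrhotic 98% on 12 weeks; cirrhotic 92% on 12 weeks, 96% on 24 weeks):

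| Cirrhotic | Of these on 24 weeks | Crude OR |
|---|---|---|
| 5 | 3 | 0.55 |
| 10 | 2 to 10 | 0.73 to 0.49 |
| 20 | 8 | 0.91 |
| 20 | 4 | 1.00 |
| 30 | 15 | 1.11 |
| 30 | 10 | 1.23 |

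All fall below the within-cirrhosis value of 2.09; whether the direction reverses depends on the mix.

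**What output tis would usually show.** In the 53-patient mix with no RBV effect:
- Expected failures are 12×0.04 + 10×0.08 + 23×0.01 = 1.51.
- The probability of no failure is 0.96^12 × 0.92^10 = 0.266 with RBV and 0.99^23 = 0.794 without.
- A finite OR needs a failure on both sides: (1-0.266) × (1-0.794) = 0.15. So about 85% of studies give none.
- The raw comparison goes against RBV in 65% of studies and in its favour in 14%; in the other 21% there are no failures at all. Finite ORs below 1 occur in about 7% and above 1 in about 8%.
- Likelihood-ratio rejection in simulation was about 3%; Wald tests rejected in at most 0.2%.

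For duration (42 non-cirrhotic, 6 cirrhotic on 12 weeks, 4 on 24 weeks), about 89% of simulated studies had no finite OR.

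**The case against.** The strongest reply is that sparsity, more than bias, will dominate the output. This stands in part. A finite reversed OR would seldom be printed, and at the cited rates there is no inflation of significant results. A reader might infer a high false-positive rate. Rejection of 21% to 46% does appear if response is assumed lower in the RBV-treated groups while G1b stays at 98-99%, but the documents supply no such set of rates, and the SAP sets no alpha for these models.

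A reader might also infer that genotype and cirrhosis fix both variables. They do not. The CP rules fix RBV only in genotype 4 and cirrhotic G1a; duration is not a CP criterion. Giving RBV to every non-cirrhotic G1a patient and to no G1b patient is close to a worst case, which is why the RBV range runs up to 0.9.

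The plan has some protection. The analyses are labelled exploratory, Protocol 9.9 names uncontrolled confounding, the primary SVR12 rates are stratified by genotype and cirrhosis, and regimen is tabulated by genotype with cirrhosis and by genotype with prior treatment (SAP 4.2.5). None of this changes the two crude estimates. Genotype, cirrhosis and prior treatment appear in the list only as separate univariate rows. The adherence models combine covariates but define no adjusted estimate for RBV or duration. The layout of tis is in SAP Part II, which is not among the documents reviewed, so a footnote there cannot be ruled out.

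**Conclusion.** The concern holds for an exploratory output. The crude RBV OR is about 0.2 to 0.9 across the assumed mixes even when RBV helps non-cirrhotic G1a with an OR of 2.1 to 3.6. The crude duration OR is about 0.5 to 1.2 against 2.1 within cirrhosis: always attenuated in these examples, reversed only in some. These sizes rest on the protocol's trial rates carrying over to routine practice, on assumed patient mixes and, for duration, on the assumed 98%. Failures could be more frequent than shown, because HCV RNA still missing after imputation counts as failure (SAP 4.2.3).

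The documents do not support the stronger readings that the odds ratios will regularly appear as significant reversed effects, or that duration is reversed whatever the mix. Nor do they support stratifying duration by genotype and cirrhosis alone: Protocol 7.1 links the 24-week result to prior null response, so confounding would remain within cirrhotic G1a. The primary SVR12 analysis is not affected.

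**What to change.** - Remove RBV use and planned duration from the pooled univariate list and from output tis.
- For RBV, show SVR12 n/N with Wilson 95% confidence intervals by RBV use within each genotype-by-cirrhosis group where both options occur. If a single summary is wanted, use an exact stratified odds ratio over those groups only, labelled exploratory.
- For duration, show SVR12 n/N by planned duration within groups of genotype, cirrhosis and prior treatment status or response where both durations occur. Give no pooled odds ratio.
- Add a footnote that genotype 4 and cirrhotic G1a carry no RBV contrast in the CP, and that the remaining comparisons are open to confounding by indication.
- Declare that the by-group regressions of Protocol 9.7.3.3 have been replaced.

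The cost is SAP wording and two small cross-tables from data already collected; prior treatment and its outcome are recorded (SAP 4.2.6.3). The downside is that many cells will be small or empty, so the report will often have to say that the effect of RBV or duration cannot be estimated.

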4.2.5 Patient Disposition

The frequencies of patients belonging to the different populations (i.e. EP, TP, CP, CPSFU; SP) will be summarized by genotype and cirrhosis status and overall using the EP analysis groups as specified in section 4.2.1. The reasons for exclusion from a particular population will be also summarized in the frequency tables. Additionally, information on patient disposition will be listed.

Furthermore the frequency of patients not completing the study as defined per protocol (i.e. no HCV RNA assessment performed at least 10 weeks post-treatment), will be summarized by treatment regimen and cirrhosis status and additionally by genotype and cirrhosis status and overall for the SP and CP. The reasons for not completing the study as entered on the CRF will be displayed (i.e. failure to return, insufficient virological response (HCV RNA detectable at end of treatment, relapse post-treatment), patient never started treatment, withdrawn consent, death, other).

Additionally, the main reason for early termination of the ABBVIE regimen (AE or SAE [Physician decision], virological non-response [Physician decision], rebound or breakthrough [Physician decision], resistance to DAA [Physician decision], patient refused to continue treatment, patient withdrew consent to participate in the study, lost to follow-up, other, unknown [if actual duration is shortened for more than 7 days]) and Ribavirin (Anemia, Nausea/Vomiting, Rash, Other) will be summarized by treatment regimen and cirrhosis status and additionally by genotype and cirrhosis status and overall for the following different analysis populations: CP and SP.

Finally the study regimens assigned at baseline will be summarized (a) by genotype and cirrhosis status and (b) by genotype and pre-treatment status (treatment naïve vs treatment experienced) for CP and SP.

An overview of Tables is given in Table 5.

Table 5 Overview of Outputs for Patient Disposition

Output Title	Output Short Name	Analysis Population
Patient Disposition by Genotype and Cirrhosis Status – EP - <country>	tdis_<c>_gc_ep	Patients Enrolled
Listing of Patient Disposition - EP- <country>	ldis_<c>_ep	Patients Enrolled
Premature Termination of the Study and its Main Reason by <Treatment Regimen/ Genotype> and Cirrhosis Status - CP - <country>	tps_<c>_<t/g>c_cp	Core population

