In addition to the summary statistics of the adherence variables, logistic regression analyses will be performed for the following adherence variables: "adherence to ABBVIE regimen" in all patients of the CP, "adherence to ribavirin" in all patients of the CP taking RBV, each categorized as follows: >=95%, >80%-<=95%, <=80% to investigate the additional impact of overall treatment adherence on SVR12. The categories may be changed if they are sparsely filled. Adherence will be included as mandatory covariate in addition to the baseline explanatory variables already mentioned above. Also the same methods will be applied as described above.

An overview of Tables is given in Table 7.

Table 7 Overview of Outputs for Primary and Secondary Effectiveness Analysis

Output Title	Output Short Name	Analysis Population
Virological Response Rates by Genotype and Cirrhosis Status – CP/CPSFU - <country>	tvr_<c>_gc_cp	Core population/ Core population with sufficient follow-up data
Virological Response Rates by Genotype and Cirrhosis Status in Patients who Completed ABBVIE Regimen – CP/CPSFU - <country>	tvr_<c>_gc_cp_ARC	Core population/ Core population with sufficient follow-up data: patients who completed ABBVIE regimen
Virological Response Rates - NCP - <country>	tvr_<c>_ncp	Non-core population
Relapse Rates by Genotype and Cirrhosis Status – CP - <country>	trr_<c>_gc_cp	Core population
Viral Breakthrough by Genotype and Cirrhosis Status – CP - <country>	tvb_<c>_gc_cp	Core population
Non-Response Rates by Genotype and Cirrhosis Status – CP - <country>	tnrr_<c>_gc_cp	Core population
Non-Response Rates by Genotype and Cirrhosis Status in Patients who Completed ABBVIE Regimen – CP - <country>	tnrr_<c>_gc_cp_ARC	Core population: patients who completed ABBVIE regimen
Impact of Patient and Disease Characteristics on SVR12 – CP - <country>	tis_<c>_cp	Core population
Adherence by Genotype and Cirrhosis Status - CP - <country>	tah_<c>_gc_cp	Core population
Adherence by Treatment Regimen and Cirrhosis Status - SP - <country>	tah_<c>_tc_sp	Safety population
Impact of Adherence to ABBVIE Regimen on SVR12 – CP - <country>	tiaa_<c>_cp	Core population
Impact of Adherence to Ribavirin on SVR12 in patients taking RBV – CP - <country>	tiar_<c>_cp_RBV	Core population: patients taking RBV

The layouts of the tables mentioned above are provided in Part II of the SAP (Table Shells).

4.2.7.2.2 *Quality of life*

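### The planned adherence score is partly set by the outcome it is meant to explain, so the SVR12 adherence regressions measure exposure and need an actual-duration counterpart

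*SAP*

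**What the plan says.** SAP 4.2.7.2.1 (Adherence) defines adherence to the ABBVIE regimen as "adherence=cumulated number of pills taken /(initial prescribed number of pills x planned duration" and adherence to ribavirin as "adherence=cumulated dose taken /(initial prescribed dose x planned duration". In both, the denominator is the dose for the whole planned course. This matches Protocol 9.3.2, which takes cumulative dose over target dose.

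The same SAP section enters each score in a logistic regression on SVR12, cut at 95% and 80%. The populations are all CP patients for the ABBVIE regimen and CP patients taking ribavirin for ribavirin. On the model it says: "Adherence will be included as mandatory covariate in addition to the baseline explanatory variables already mentioned above". On the bands it says: "The categories may be changed if they are sparsely filled".

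Three other provisions matter:
- SAP 4.2.5 lists the reasons for ending the regimen early. They include "virological non-response [Physician decision], rebound or breakthrough [Physician decision], resistance to DAA [Physician decision", and also loss to follow-up.
- SAP 4.2.3 counts an SVR12 value that is still missing after flanking and backward imputation as a virological failure.
- SAP 4.2.1 removes losses unrelated to safety or effectiveness from CPSFU, but not from the CP.

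**The concern.** Secondary objective 2 in the protocol asks how adherence influences treatment outcome, and these regressions are the only inferential analyses that serve it. A covariate meant to explain SVR12 should not itself be produced by SVR12 failure. Here it can be, in two ways.

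1. Virological failure ends treatment, and the shortened course lowers the score even though every pill due was taken.
2. Loss on treatment lowers the score and, if no later HCV RNA value exists, also creates the failure by imputation.

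Baseline covariates cannot correct either, because the distortion arises after baseline. At stake is reading a failure of the regimen, or a loss to follow-up, as a consequence of poor pill-taking. Ribavirin dose reductions, and stops for adverse events or refusal, are real under-exposure and are not part of this point.

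**Working it through.** The plan gives no power or effect-size figure for this analysis, so there is nothing to reproduce.

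**Score of a full pill-taker stopped on day d.** The score is d divided by planned days (84 or 168, from the 12- and 24-week courses).
- 12 weeks: 67/84 = 79.8% and 68/84 = 81.0%, so a stop by day 67 falls in the lowest band. 79/84 = 94.0% and 80/84 = 95.2%, so days 68-79 fall in the middle band and day 80 onwards in the top band.
- 24 weeks: 134/168 = 79.8% and 135/168 = 80.4%, so a stop by day 134 falls in the lowest band.

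**The same patient scored to the actual last dose.** Stopped at day 42 of 84, the planned score is 50% and the duration percentage is 50%. The ratio is 100%.

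**Does any planned output cover this?** The CPSFU repeat in SAP 4.2.7.1 concerns the primary analysis. The completer tables in 4.2.7.2.1 concern response rates and non-response categories. The stop-reason and duration tables are descriptive. Table 7 lists the adherence-impact outputs only for the CP and for CP patients taking ribavirin.

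**Illustration (assumed counts, n = 53).** There are three failures in all. Fisher's test is used for illustration and is not planned; odds ratios for failure add 0.5 to each cell.

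| Early cases among the three failures | Cut | Failures, low v rest | Odds ratio | p |
|---|---|---|---|---|
| One virological stop, one recorded loss | 80% | 2/2 v 1/51 | 168 | 0.002 |
| Same, plus 9 other low scorers | 95% | 2/11 v 1/42 | 7.3 | 0.11 |
| One virological stop only | 80% | 1/1 v 2/52 | 61 | 0.057 |
| Same, plus 9 other low scorers | 95% | 1/10 v 2/43 | 2.6 | 0.47 |

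**Simulation with no true adherence effect.** There were 4,000 runs with n = 53 and pill-taking independent of outcome (Beta(60,2), so about 18% score 95% or less while on treatment). Stop time is uniform over 20-95% of the course. Every on-treatment failure stops early, and every loss has intake recorded. No baseline covariates are fitted. All rates are assumptions.

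| Setting: virological failure / share on treatment / lost on treatment / early stop with SVR12 | Fisher p<0.05, 80% cut | Fisher p<0.05, 95% cut | Median odds ratio, 95% cut: planned v actual duration |
|---|---|---|---|
| A: 4% / 25% / 0 / 0 | 21% | 6.5% | 2.9 v 1.4 |
| B: 5% / 50% / 0 / 0 | 51% | 22% | 6.4 v 1.4 |
| C: 5% / 50% / 4% / 0 | 86% | 66% | 12.1 v 1.2 |
| D: 4% / 25% / 0 / 4% | 11% | 4.4% | 2.3 v 1.4 |

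Fisher's rate with actual duration is 1-2% at the 95% cut. Expected virological stops per study are 53 × 0.04 × 0.25 = 0.53 in A and D, and 53 × 0.05 × 0.50 = 1.33 in B and C. C adds 53 × 0.04 = 2.12 losses.

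**Simulation with a true effect.** Failure is 20% below and 2% above the 95% cut, so the odds ratio is (0.20/0.80)/(0.02/0.98) = 12.2 (about 12). Half of failures occur on treatment and 4% of patients are lost. Median odds ratios:
- planned formula: 35 in the CP, 21 in CPSFU12
- actual duration: 4.9 in the CP, 11.4 in CPSFU12

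Only actual duration in CPSFU12 comes near the true value. In the CP, imputed failures unrelated to pill-taking dilute the effect.

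**The case against.** The strongest reply is that the SAP does what the protocol says. Dose received over target dose is a legitimate quantity, and overall treatment adherence can be read to include finishing the course. That stands. A reader might infer an error in the formula or a departure from the protocol; the documents support neither. The fault lies in interpreting the score as pill-taking behaviour.

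The second reply concerns size, and much of it stands:
- The highest rates, at the 80% cut, rest on a low band of one or two patients. The SAP allows sparse bands to be changed, so the 95% cut is the likelier analysis.
- In setting A, 0.99^53 = 59% of studies contain no on-treatment virological failure at all.
- Stopping is a physician decision and the documents do not say that every on-treatment failure stops early. If half do, setting B at the 95% cut falls from about 22% to about 8%.
- Setting C needs recorded intake, because adherence is not imputed. With no losses recorded it falls to about 24%; with half recorded, to about 46%.

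Third, the cases will be visible. Stop reasons, a disposition listing, non-response categories and treatment duration are all reported. This helps a reader but does not correct the regression.

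One stronger reading should be resisted. For baseline covariates the SAP says "categories could be combined, if their impact on SVR12 is similar", and after the adherence paragraph it adds "Also the same methods will be applied as described above". A reader might infer that adherence bands will be merged after sight of SVR12. That is only one reading: the similarity rule refers to categories listed before it, and adherence has its own rule based on sparseness.

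**Conclusion.** The point holds as a limitation of interpretation that should be fixed. Both mechanisms follow from the SAP text, and no planned analysis removes them from the regressions that serve secondary objective 2.

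The size is uncertain because the documents give no rates for on-treatment failure or loss in this cohort. At the 95% cut the distortion is small in the mild settings (about 4-7% false positives, median odds ratio about 2-3). It is large, with an odds ratio above 10, when recorded on-treatment losses also occur. It would be wrong to infer that a false association is assured: many plausible studies of 50-55 patients would contain no such case, or one.

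Nor should a reader infer a threat to the main result. The regressions are declared exploratory, and the primary SVR12 estimate does not use the adherence score.

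**What to change.** 1. Keep the planned regression on percent of target dose, and label it as exposure.
2. Add one regression on adherence up to the actual last dose. For the ABBVIE regimen this is percent of target dose divided by a variable already planned in the same section: "Percentage of actual treatment duration in relation to the target duration of ABBVIE regimen taken". Show early discontinuation by reason beside it.
3. Run both regressions in the CP and in CPSFU12. Actual duration in the CP alone dilutes a true effect.
4. State that sparse adherence bands are merged on category counts only, without sight of SVR12.

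Do not add an analysis that excludes virological stops. It selects on the outcome and can remove a real effect where missed pills caused the breakthrough. If every failure is on treatment, it leaves no failures to analyse.

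The cost is a few extra exploratory outputs, with no new data and no change to the protocol-defined variable. The drawbacks should be stated. The apparent effect may shrink. A patient who quits early by choice can score 100% on the new measure, which is why discontinuation by reason sits next to it. Patients with no end-of-treatment date or no intake data cannot be scored.
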